7.5 Randomization

It is anticipated that a total of 306 subjects will be randomized to one of the two treatment groups. Once a subject has provided informed consent and eligibility criteria have been confirmed, the site-designee will access the secure, study website to randomize the subject and receive the subject's assignment number. While the subjects, Investigator, and Sponsor are not blinded to treatment assignment due to study implementation requirements, aggregated data will remain blinded to all until the database is locked.

Subjects will be randomized by site in a 1:1 ratio to receive either tele-rehab-supported PT or traditional home and/or clinic-based PT. In either case, randomization must occur no less than 10 days prior to the patient's surgery date, or the patient will be considered ineligible.

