9 GENERAL METHODOLOGY

Descriptive statistics will be grouped into three categories: Tele-rehab PT, Traditional PT, and Overall. Continuous variables will be summarized by the number of observations and the mean, standard deviation, median, minimum, and maximum values. For categorical data, the counts, denominators and percent per category will be presented within non-missing observations. Subjects with a missing value for a variable will not be included in the calculation for that variable. All continuous data will be summarized with one more significant digit than in the dataset. Percentages will be rounded to one digit to the right of the decimal. Subjects with missing categorical data will not be included in calculations of percentages for that variable unless otherwise specified. No imputation will be made for missing values. Both the frequency and the associated denominator will be shown to facilitate review of missing categorical data. Categorical responses of "Unknown" will be set to missing.

It is anticipated that both the 6- and 12-week follow-up calls will not occur exactly at 6 and 12 weeks post-op, respectively, for every patient. However, the DCRI Call Center is instructed to contact subjects as close as possible to the appropriate time since postoperative discharge date. Data needed for the primary endpoint will be prioritized if patients agree to spend only a limited time on the follow-up call.

All statistical tests will be one-sided (non-inferiority) or two-sided (superiority) with a significance level of 0.05, unless otherwise documented. Tests for differences between treatment groups for endpoints that are not protocol-specified may be performed. Unless otherwise stated, continuous variables will be compared between groups with two-sample student t-test or with Wilcoxon's rank-sum test depending on normality assumptions.

When it is necessary to detect differences between groups, unless it is stated otherwise, categorical values will be compared using the chi-square test or Fisher's exact test. The chi-square test will be used when all cells in the table of the categorical comparison have an expected value of 5 or above. Otherwise, a Fisher's exact test will be performed.

All tables will be presented with summary statistics overall and by treatment group unless otherwise specified.

All analyses will be completed using SAS version 9.4 or higher.

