9.9 Power and Sample Size Calculations

The primary aim of this study is to assess the difference in outpatient post-surgical costs between the control and intervention groups at 12-weeks post-operative. The exact post-procedure cost estimates under study are unknown; however, we can estimate that an effect size of approximately 0.33 can be detected with 150 subjects per group with at least 80% power. The effect size is the ratio of the mean difference over the standard deviation (SD) assumed for each population. Lower variability would enable detection of a smaller cost difference, or the detection of a larger difference with fewer patients. The sample size estimates were made assuming a two-sample t-test with equal variance and a significance level of 0.05. Thus, with 300 subjects we can detect an effect size of 0.33 which represents a whole scenario of cost differences that can be detected with at least 80% power that is dependent on the variability of the costs under study. The below table illustrates some example cost differences that could be detected based on the assumed SD of the costs.

Standard Deviation (SD)	Mean Cost Difference (\$)	Standard Deviation (SD)	Mean Cost Difference (\$)
100	32.50	800	259.60
200	64.90	900	292.10
300	97.40	1000	324.50
400	129.80	1100	357.00
500	162.30	1200	389.50
600	194.70	1300	421.90
700	227.20	1400	454.40
750	243.40	1500	486.80

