The null hypothesis for the primary endpoint is that there is no treatment difference between patients who receive tele-rehab-supported PT versus traditional home and/or clinic-based PT. The alternative hypothesis is that a treatment difference exists between patients who receive tele-rehab-supported PT versus traditional home and/or clinic-based PT.

Let μ_T and μ_C be the average total health care costs for the virtual and control PT groups, respectively. The null hypothesis and the alternative hypothesis will be as follows:

$$\begin{aligned} H_0: \mu_T &= \mu_C \\ H_A: \mu_T &\neq \mu_C \end{aligned}$$

The primary statistical method for the hypothesis test will be t-test, and the mean difference between groups will be presented with a 95% confidence interval (CI). The test is two-sided even though we are more interested in determining that the intervention group is superior to the control group to allow for a possible negative significant difference.

Let \bar{X}_T and \bar{X}_C be the sample mean costs for the virtual and control groups, respectively, and let S_T^2 and S_C^2 be the sample variance for the virtual and control samples, respectively. The equality of the variances of the two samples will be tested using the Folded F-test (i.e., $F = \text{Max}(S_T^2, S_C^2)/\text{min}(S_T^2, S_C^2)$). If there is not strong statistical evidence to say that the variances of the two samples are different (insignificant F-test and 4-fold variance difference), then the alternative hypothesis for total cost will be concluded when the associated t-test statistic assuming equal variance is less than the 2.5th percentile of the Student's t distribution with $n_T + n_C - 2$ degrees of freedom, where n_T is the number of subjects in the virtual group and n_C is the number of subjects in the control group. Otherwise, the t-test will be computed assuming the variances are unequal.

If a parametric method is determined not to be possible through normality checks (Shapiro-Wilks test) or transformations, a Wilcoxon rank-sum test will be performed for the primary effectiveness endpoint and a 95% CI for the median difference presented.

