9.11.2 Safety hypothesis (Non-Inferiority Test)

The tele-rehab intervention will be non-inferior to traditional PT at 12 weeks using the following endpoints at 12 weeks:

- Pain: The minimal perceptible clinical improvement difference (MCID) for non-inferiority will be 1.7
- Re-hospitalizations: The total number of re-hospitalizations will differ by no more than 1.
- Falls: The percentage of subjects reporting any fall from index hospital discharge until 12 weeks postoperative will differ by no more than 10% (reported at 6 and 12 weeks as a categorical yes/no response).

A one-sided 95% confidence interval for the mean difference between intervention groups will be completed using parametric methods if possible; otherwise, the median difference will be utilized. Non-inferiority will be determined if the upper bound of the difference indicative of a treatment benefit in the control group is less than the MCID for each endpoint. No adjustment for multiple comparisons is necessary since all tests must be significant to determine non-inferiority (intersection-union multiple testing rule) for the safety hypothesis.

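### The median-difference fallback in SAP 9.11.2 cannot test the falls margin and changes what the pain margin is compared with; each safety endpoint needs a named estimator

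*SAP*

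**What the plan says.** SAP 9.11.2 sets three safety margins at 12 weeks. The one for pain "for non-inferiority will be 1.7". For falls, "The percentage of subjects reporting any fall from index hospital discharge until 12 weeks postoperative will differ by no more than 10" (a percentage). Re-hospitalizations may differ in total number by at most 1, without saying whether that is per patient or per arm.

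One estimation sentence then covers all three: a one-sided 95% interval for the mean difference "using parametric methods if possible; otherwise, the median difference will be utilized". The decision rule follows: "Non-inferiority will be determined if the upper bound of the difference indicative of a treatment benefit in the control group is less than the MCID". All three must pass, and the SAP relies on this to forgo a multiplicity adjustment.

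9.11.2 does not say when a parametric method counts as impossible. The only stated check is in 9.10, for cost: "If a parametric method is determined not to be possible through normality checks (Shapiro-Wilks test) or transformations". Section 9.11.1 (effectiveness) says its analyses resemble those of 9.10. Section 9.11.2 does not repeat this.

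**The concern.** The rule suits a continuous variable, but none of the three safety endpoints is one in the usual sense. A 0/1 variable has a median of 0 whenever fewer than half of patients have the event, so a median difference carries almost no information about a 10-point difference in percentages. For an integer pain score, mean and median differences separate when the arms differ in shape, yet the margin stays at 1.7.

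At stake is the safety claim. If falls cannot realistically fail, the requirement that all three pass protects less than the SAP supposes. There is no data monitoring committee (SAP 6.1) and no interim safety analysis (9.13), so this is the plan's only non-inferiority assessment of harm.

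**Working it through.** **Inputs from the documents.** Level: "All statistical tests will be one-sided (non-inferiority) or two-sided (superiority) with a significance level of 0.05". Size: "an effect size of approximately 0.33 can be detected with 150 subjects per group with at least 80% power". Allocation: "Subjects will be randomized by site in a 1:1 ratio". Margins as above. The documents give no fall rates, re-hospitalization rates or pain distribution, so those below are assumptions. Differences are intervention minus control; positive means harm.

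**The plan's own figure.** Protocol 5.1 gives power 0.8023 at effect size 0.3255 with 150 per group. The normal approximation is Φ(0.3255 × √(150/2) − 1.960) = Φ(0.859) = 0.805; the noncentral t gives 0.8023, an exact match. That figure is for cost. Neither document gives power for a safety test.

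**Would the 9.10 check be failed?** At 150 per arm, Shapiro-Wilk rejected in 99.9–100% of simulated trials for all three endpoints. Transformation does not help: a transformed yes/no variable still has two values, and for integer pain scores (several assumed gamma and rounded normal shapes, 500 runs each) the raw, square-root and log(x+1) scores failed in every run. Had a transformation been accepted, 1.7 would no longer be on the analysis scale.

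**Falls, by hand.** Take observed rates of 10% v 30%.
- Risk difference: SE = √(0.10×0.90/150 + 0.30×0.70/150) = 0.0447. Upper bound = 0.20 + 1.645 × 0.0447 = 0.274, above 0.10: fails.
- Difference of medians: 0 − 0 = 0.
- Hodges-Lehmann bound (the interval that goes with the Wilcoxon test): of 150 × 150 = 22,500 pairwise differences it is the k-th largest, with k = 22,500/2 − 1.645 × √(22,500 × 301/12) ≈ 10,014. It is 0 unless at least 10,014/22,500 = 44.5% of the differences equal +1. Here the share is 0.30 × 0.90 = 27%, so the bound is 0: passes.

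With 10% of controls falling, the bound leaves 0 only when the observed intervention rate reaches 0.445/0.90 = 49%.

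**Falls, simulated** (1,000 trials per row):

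| Control v intervention | Pass, Hodges-Lehmann | Pass, risk difference |
|---|---|---|
| 10% v 20% (at the margin) | 100% | 4.3% |
| 10% v 30% | 100% | 0% |
| 20% v 40% | 99.9% | 0.1% |
| 10% v 40% | 98.7% | 0% |
| 10% v 48% | 65% | 0% |
| 10% v 55% | 9% | 0% |

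**Pain.** Control scores are assumed to be a rounded gamma clipped to 0–10 (mean 2.24, SD 1.84). Hodges-Lehmann bounds on integer scores are whole numbers, so 1.7 acts as a cut between 1 and 2.
- 26% of intervention patients scoring 8–10 (mean difference 1.76, beyond the margin): passes 62% by median, 4.5% by mean.
- 30% doing so (mean difference 2.03): 26% v 0.1%.
- Uniform shift of 1.7: 0.3% v 5.5%.
- Uniform shift of 1.4, inside the margin (600 runs, rounded gamma with control mean about 2): 15% v 43%.

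**Re-hospitalizations.** With Poisson counts and the margin read per patient:
- 0.05 v 0.20: both rules pass 100%.
- 0.05 v 0.50: median 95.5%, mean 100%.
- 0.05 v 0.80: median 1.3%, mean 93.7%.

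The median is the more lenient rule only when stays are concentrated: 30% of patients with four stays each (mean difference 0.30 × 4 − 0.05 = 1.15) pass 100% by median and 1.2% by mean. If the margin instead refers to arm totals, equal rates of 3% to 10% give an upper bound, at an observed difference of zero, of 1.645 × √(2 × 150 × rate) = 4.9 to 9.0 stays, so that test would almost never pass.

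**The case against.** A reader might infer that the fallback is certain to be used for every safety endpoint. The documents do not say so. The Shapiro-Wilk check is written for cost and carried only into 9.11.1; 9.10 also looks at plots, tries transformations and asks for strong evidence before giving up the parametric method. Section 9 ties the normality choice to continuous variables and sends categorical ones to chi-square or Fisher's exact test. With the falls margin stated as a percentage of subjects, a sensible analyst could well bound the risk difference. That stands as a plausible reading. It does not remove the problem: chi-square and Fisher test for a difference and supply no bound to compare with 10 points, and the one sentence in 9.11.2 that does supply a bound names only mean and median differences.

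Section 7.3 also plans superiority tests for all non-inferiority endpoints. A 10% v 30% result would stand out there: z = 0.20/√(2 × 0.20 × 0.80/150) = 4.3. But that test does not govern the non-inferiority claim, so the report could call falls both non-inferior and significantly worse.

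The pain figures depend on assumed shapes; if the arms differ only by a shift, the mean and median differences target the same quantity. Hodges-Lehmann is also an assumption, since the SAP says only median difference. Both points stand.

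**Conclusion.** The point holds as a defect in the written rule. If the fallback in 9.11.2 is followed, falls would be declared non-inferior at almost any plausible rates, and pain would be judged on a different quantity from the one its margin is otherwise applied to, with error in either direction.

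Three stronger conclusions are not supported:
- That falls pass automatically: the median rule fails once the intervention-arm rate nears or exceeds one half.
- That the median makes the re-hospitalization test vacuous: at 0.05 v 0.30 per patient the mean-based bound is 0.25 + 1.645 × √(0.35/150) = 0.33, which also passes. The margin of 1, read per patient, is the main cause.
- That KOOS, range of motion and gait speed in 9.11.1 are harmed by the same sentence: nothing here shows it.

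The sizes rest on 150 analysed per arm, the assumed rates and distributions, and Hodges-Lehmann as the median interval. These are secondary endpoints and the primary cost conclusion is unaffected, so this should be fixed rather than must be.

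**What to change.** In SAP 9.11.2, delete the median fallback and name one estimator per endpoint, each with a one-sided 95% upper bound:
- **Falls:** risk difference (Newcombe or Miettinen-Nurminen) against 10 percentage points.
- **Pain:** difference in means (Welch or bootstrap) against 1.7, whatever the normality result.
- **Re-hospitalizations:** difference in mean count per patient (bootstrap or robust Poisson), with the unit of the margin of 1 stated.

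In the simulations, using simple normal-theory bounds, tests on these scales pass at or near the margin in about 4–8% of trials: falls 4.1–4.3%, pain 4.5–5.5%, re-hospitalizations (0.05 v 1.05 per patient) 7.7%.

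The change is to wording only, with the same data and sample size. The price is that falls can now realistically fail. With equal rates p in both arms, power is Φ(0.10/√(2p(1−p)/150) − 1.645): 99% at p = 5%, 89% at 10%, 78% at 15% and 70% at 20%. The number per arm for 80% power, (1.645 + 0.842)² × 2p(1−p)/0.10², is 59, 112, 158 and 198.

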9.12 Other Exploratory Analyses

The final objectives (exploratory analyses) are to determine if superiority between PT methods exist for the endpoints primarily tested for non-inferiority, determine whether individual patient characteristics are associated with differential improvement from 6 to 12 weeks assessed by patient-reported outcomes, and to determine the cost for the VERA system such that the cost between the control group and intervention groups is cost-neutral, assuming that the intervention group is determined to cost less. The secondary endpoints that will be considered are detailed in Sections 7.2-7.4.

An appropriate regression model may be considered for the primary cost endpoint to adjust for baseline variables found to be imbalanced or to assess the influence of site on treatment effects. This will be done by adding a fixed-effect main site effect and interaction term between randomization strata (site) and treatment in a generalized linear model. Assuming the average cost for the intervention group is lower than the control group, we will also determine the cost for the VERA system such that the cost difference between the control group and the intervention group is cost-neutral.

If the endpoints tested for non-inferiority between PT methods are found to be non-inferior, then additional analyses to control for baseline covariates or site effects may be done using methods previously described to determine if the PT group is superior to the control group after adjustment.

To determine whether individual patient characteristics are associated with differential improvement, we will evaluate the change over time (0-6, 0-12 and/or 6-12 weeks) for endpoints measured at multiple time points using parametric or non-parametric methods previously discussed. When both 6 and 12-week assessment are made, the Sidak alpha-correction method will be used to correct for multiple comparisons. The correction method is given by $1-(1-\alpha)^{1/k}$, where k is the number of comparisons considered. If adjustments for baseline covariates are necessary, generalized repeated measures models will be used to assess main effects of intervention group and time, as well as the interaction between time and intervention groups.

Progress toward recovery goal will be compared between PT groups using either a chi-square or Fisher's exact test for categorical responses (score=10 yes/no), Wilcoxon rank sum test for actual score and change from baseline score, and as time until meeting recovery goal (score=10) using the nonparametric log-rank test or Cox proportional hazards model.

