6.2 Study Objectives

6.2.1 Primary Objective:

The primary objective is to compare the effects of tele-rehab-supported PT versus traditional home and/or clinic-based PT for TKR on health service use costs at 12-weeks postoperative.

Hypothesis (Superiority Test): Patients who receive tele-rehab-supported PT will have lower total episode of care costs compared with patients in the traditional PT group at 12-weeks.

6.2.2 Secondary Objective:

The secondary objectives are to compare tele-rehab-supported PT and traditional PT on patient-centered outcomes as follows:

- a. Effectiveness hypothesis (Non-Inferiority Test): The tele-rehab intervention will be non-inferior to traditional PT at 6 weeks (differences between groups <5% for clinical and patient-reported outcomes) and 12 weeks (difference <5% patient-reported outcomes).
- b. Safety hypothesis (Non-Inferiority Test): The tele-rehab intervention will be non-inferior to traditional PT at 12 weeks (pain, falls, and self-reported number of re-hospitalizations).

6.2.3 Exploratory Objectives:

The final objectives (exploratory analyses) are to determine if superiority between PT methods exist for the endpoints primarily tested for non-inferiority, determine whether individual patient characteristics are associated with differential improvement from 6 to 12 weeks assessed by patient-reported outcomes, and to determine the cost for the VERA system such that the cost between the control group and intervention groups is cost-neutral, assuming that the intervention group is determined to cost less.

7 Study Design

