9.10 Primary Effectiveness Analysis

The total health service use costs at 12-weeks post-operative will be compared between patients who receive tele-rehab-supported PT (virtual group) versus traditional home and/or clinic-based PT (control group) for TKR. The primary cost comparisons will be done using an analysis of variance (ANOVA) method for continuous variables if (1) the dependent variable is normally distributed or (2) can be normalized using a transformation such as the logarithm or square root. The underlying assumptions of the statistical test procedure will be verified through non-normality tests and plots. If there is strong evidence that the assumptions are not met or cannot be met with an appropriate distribution, the nonparametric Wilcoxon Rank sum test will be used.

The total health service use costs at 12-weeks post-operative will be the primary effectiveness endpoint for this study. This will be calculated using a fee-for-service model and assigned costs. Tele-health for rehabilitation services was not a reimbursable service at the start of the trial, and thus a total intervention cost, including direct and indirect time with physical therapy and any in-person visits, is assigned using the following units and costs:

Healthcare Encounter	Unit	Cost
Intervention	Total (all interactions)	\$600
Home health PT	<5 visits (cost per visit) ≥5 visits (single cost per 60-day episode)	\$133 \$2,325
Outpatient clinic PT	Single visit	\$90
PT call/email	Single interaction	n/a
Doctor's office	Single visit	\$150
Doctor's office call/email	Single interaction	n/a
Urgent care or ER visit	Single visit	\$250
Re-hospitalization	Full length of one inpatient stay	\$7,825
Inpatient rehab facility	Full length of stay	\$10,720
Skilled nursing facility	Full length of stay	\$6,510

Intervention Group Patients: Total costs will be calculated as the assigned cost of the intervention plus assigned costs for any reported doctor's office visits, urgent care or ER visits, re-hospitalizations, and inpatient rehabilitation or skilled nursing facility stays in the 12 weeks following discharge from the surgical hospital stay. The formula is as follows:

Cost = intervention cost + (# of doctors office visits * \$150) + (# of ER/UC visits * \$250) + (# of re-hospitalizations * \$7,825) + (# of skilled nursing facility stays * \$6,510) + (# of inpatient rehabilitation facility stays * \$10,720)

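### The cost-neutral price is labelled as VERA's, but the cost formula prices the whole intervention package; it is also produced only when favourable and without an interval

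*SAP*

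**What the plan says.** SAP 6.2.3 lists the cost-neutral price among the exploratory objectives, with the condition "assuming that the intervention group is determined to cost less". SAP 9.12 repeats it: "Assuming the average cost for the intervention group is lower than the control group, we will also determine the cost for the VERA system". The condition there is thus a lower average, and the price sought is the one that makes the arms cost-neutral. Neither section gives a formula, an interval or a sensitivity range.

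The only intervention price is in SAP 9.10, where "a total intervention cost, including direct and indirect time with physical therapy and any in-person visits, is assigned". The cost table sets it at $600 per patient, as one total for all interactions. The intervention-arm formula begins "Cost = intervention cost + (# of doctors office visits" and continues with emergency or urgent care visits, re-hospitalizations and facility stays. It has no separate term for the platform, for therapist time or for in-person PT.

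For the primary comparison, SAP 9.10 plans a 95% CI for the mean cost difference. It also allows a transformation, or a Wilcoxon test with a CI for the median difference. Neither interval is linked to the cost-neutral price.

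**The concern.** There are three issues.

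- **Label and input differ.** Protocol 3.4.1 uses the VERA name for the motion-tracking platform installed in the home. The $600 covers more than that. Setting the arms equal and solving for the one intervention term gives the price of everything in that term.
- **The figure appears only in one direction.** If the intervention arm costs more, a break-even below $600 would be just as informative, but none is planned. The two conditions also differ: 9.12 requires a lower average, while the wording of 6.2.3 could mean a significant result.
- **No interval is planned**, so the price would appear as a single value.

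What is at stake is a price threshold for a product that the sponsor developed. Purchasers could read it directly as what the platform is worth. If it includes money needed for therapists, they would be misled by that amount.

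**Working it through.** **Inputs.** Assigned intervention cost $600 (SAP 9.10). 150 per arm, two-sample t-test with equal variance, significance level 0.05, and a detectable difference of $486.80 at SD $1,500, the largest SD tabulated (SAP 9.9). Two-sided test (SAP 9.10). The split of the $600 is not in the documents, so shares are assumed below.

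**The plan's own figure.** At SD $1,500, 486.80 / 1,500 = 0.3245. The noncentrality is 0.3245 × √(150/2) = 2.81, and power is 80.0% (exact t) or 80.2% (normal approximation). The stated 80% is reproduced. The documents give no break-even figure to reproduce.

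**Break-even.** Write the mean intervention cost as P + M, where P = 600 and M is the mean of all other terms. Cost neutrality requires P* + M = mean control. Hence P* = 600 + (mean control − mean intervention). P* replaces the whole $600 term, so it is the package price. The platform price is P* minus the non-platform part of the $600.

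With a saving of $486.80, P* = $1,086.80:

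| Assumed non-platform share of $600 | Overstatement if P* is called the platform price | Platform break-even |
|---|---|---|
| 0% | $0 | $1,087 |
| 25% | $150 | $937 |
| 50% | $300 | $787 |
| 75% | $450 | $637 |

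**Interval.** P* is the mean difference plus a constant, so its SE is that of the difference: 1,500 × √(2/150) = $173.2. With 298 df the 95% half-width is 1.968 × 173.2 = $341. At the design saving this gives about $746 to $1,428. The half-width is 57% of the $600 and 31% of $1,087. At SD $600 it is $136; at SD $1,000 it is $227.

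The actual cost SD is unknown and could exceed $1,500. Re-hospitalization at $7,825 alone contributes 7,825 × √(0.05 × 0.95) = $1,705 at an assumed 5% rate. At an assumed SD of $2,500 the half-width is $568.

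**Reporting only when favourable.** Let D be the true saving.

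- Lower-mean trigger: upward bias = SE × φ(D/SE) / Φ(D/SE).
- Significance trigger: upward bias = SE × φ(1.96 − D/SE) / [1 − Φ(1.96 − D/SE)].

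At SD $1,500:

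| True saving | Bias, lower-mean trigger (9.12) | Bias, significance trigger (possible reading of 6.2.3) |
|---|---|---|
| $0 | $138 | $405 |
| $243 (half the design saving) | $28 | $205 |
| $487 (design saving) | $1 | $60 |

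**The case against.** A reader might infer that the reported price will be overstated. The documents do not support that. They contain no break-even formula, and the overstatement arises only if the package figure is presented as a platform price. Its size cannot be found from the documents. That the $600 includes the platform is itself inferred from its being a total; 9.10 does not name the platform. If the platform lay outside the $600, its break-even would be the saving alone ($486.80 in the example) and the figure would not have to exceed $600.

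The label may be loose terminology. SAP 7.1 attaches the Vera name to the whole tele-rehab arm in one place, and elsewhere in the same section distinguishes VERA from the virtual PT support that goes with it. This makes the target ambiguous rather than plainly wrong, which is a reason to define it.

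A reader might also infer a material selection bias. Under the 9.12 trigger it is about $1 at the design saving; it matters only if the true saving is small or the trigger is significance. It is also a bias over repeated trials and does not show that a particular reported price is too high.

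Finally, the analysis is exploratory, its condition is stated in advance, SAP Section 4 places exploratory analyses outside the plan's scope, and the planned CI for the mean difference could be shifted by $600. These points lower the importance. They do not settle which quantity is priced, and the shift fails if the primary analysis uses a transformed scale or a median difference.

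**Conclusion.** The point holds as a minor one. The formula gives a break-even for the whole intervention package, while 6.2.3 and 9.12 name the VERA system. Reporting one as the other would overstate the price by the non-platform part of the $600: $0 to $450 over the assumed shares of 0% to 75%. The favourable-only rule adds an upward bias of $138 falling to $1 as the true saving rises from zero to the design value, under the lower-mean trigger. The unplanned interval would be about ±$341.

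The dollar figures assume SD $1,500 in both arms, 150 per arm and an approximately normal mean difference. It is also assumed that no further cost definition stands in the part of 9.10 directly after the intervention-arm formula, which could not be checked. Neither the primary cost comparison nor any non-inferiority conclusion is affected.

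**What to change.** In SAP 6.2.3 and 9.12:

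1. Define the target as the break-even price of the whole intervention package, 600 + (mean control − mean intervention), using arithmetic mean costs.
2. Report it whatever the sign of the difference and whichever primary test is used. This also removes the unclear trigger.
3. Give a 95% CI, by bootstrap if costs are skewed. Cost neutrality concerns arithmetic means, so a CI for a median difference or on a transformed scale cannot be shifted to a price.
4. Quote a price for the VERA platform only after subtracting a stated non-platform component of the $600, or a range for it.

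The cost is a few sentences in the SAP and slightly more analysis, with no new patient data. A platform price needs a stated split or range from the study team. The drawback for the sponsor is that the quoted price may be less favourable.
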